#### **Retrospective analysis of patients who received a fully artificial heart.**

The duration of the intervention in each group will be 72 hours. Each Jaftron / CytoSorb Removal Column can be used within 24 hours, so all patients in 2 groups use 3 filters during the study.

Researchers will collect demographic, clinical and laboratory data from patients before, during and after surgery.

The incidence of early cellular or humoral rejection, the duration of ventilation, intensive care and hospital stay, the use of vasopressors and inotropes in the perioperative period, and the incidence of perioperative complications and survivals will be documented.

The level of cytokines (IL-1, IL-6, IL-8, IL-10, tumor necrosis factor alpha) and complements will be determined before, during and after the use of the extracorporeal life support system for heart and pulmonary failure; surgery on the aortic arch, patients on mechanical circulatory support, if investigators find a corresponding difference between the two groups in terms of clinical variables.

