### Performance evaluation criterias

| Extracorporeal life support system with pulmonary and / or heart failure |
|---|
| Primary results  |

|                          |   |
|--------------------------|---|
| 1                 | Cytokine response [Time: 24-48 hours]

The level of pro- and anti-inflammatory cytokines (IL-1, IL-6, IL-8, IL-10, tumor alpha-factor) before the implantation, 2 hours after the start of ECMO support, explantation of ECMO, 24 hours after explantation of ECMO.     |
| 2                 | SOFA-Score [Time Frame: 24, 48, 72 hours]

Sequential Organ Failure Assessment Score at 24, 48, 72 h (values from 6 to 24, where the higher values explain higher disease severity)   |
| 3                 | Difference of mean arterial pressure [Time Frame: 24, 48, 72 hours]

Comparison of mean arterial pressure at 24, 48, 72 hours between between two interventions (CytoSorb and Jafron)   |
| 4                 | Difference of CVP [Time Frame: 24, 48, 72 hours]

Comparison of CVP at 24, 48, 72 hours between between two interventions (CytoSorb and Jafron)   |
| 5                 | Serum lactate [ Time Frame: 24, 48, 72 hours ]

Level of serum lactate at 24, 48, 72 h  |
| 6                 | 
 
Days on ventilator, vasopressor and renal replacement therapy [ Time Frame: until day 30 post-surgery ]
 

Total days on ventilator, vasopressor and renal replacement therapy within 30 days post-surgery will be assessed |
| 7                 | Doses of vasopressors and / or inotropes ( $\mu\text{g} / \text{h} / \text{kg}$ bodyweight) [Time: first 72 hours]  |
| Secondary results |   |
| 1                 | Inflammatory response - The level of C-reactive protein (CRP) [Time: 24-48 hours]

The level of C-reactive protein (CRP) before the start of ECMO, 2 hours after the implantation of ECMO, during ECMO, 24 hours after ECMO explantation.                        |
| 2                 | Inflammatory response - The level of leukocytes [Time: 24-48 hours]

The level of leukocytes before the start of ECMO, 2 hours after the implantation of ECMO, during ECMO, 24 hours after ECMO explantation.   |

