| 3                 | Inflammatory response - The level of procalcitonin [Time: 24-48 hours]

The level of procalcitonin before the start of ECMO, 2 hours after the implantation of ECMO, during ECMO, 24 hours after ECMO explantation.   |
| 4                 | Level of leukocyte [Time: 24-48 hours]

Level of leukocyte cells in the bloodstream at 24, 48 hours.  |

|                          |  |
|--------------------------|--|
| 5                 | Application and dosage of vasopressors [Deadline: first 48 hours]
Incidence of application and level of dosage of vasopressors on days 2 and 3 after surgery; |
| 6                 | Application and dosage of inotropes [Deadline: first 48 hours]
Incidence of application and level of dosage of inotropes on days 2 and 3 after surgery;       |
| Long-term results |  |
| 1                 | Length of stay in the intensive care unit [Duration: first 48 hours]   |
| 2                 | Length of hospital stay [Term: up to 1 month];   |
| 3                 | 30 day survival rate.  |

| Patients with left ventricular assist device implantation |  |
|--|--|
| Primary results   |  |
| 1   | Difference of Cytokine response [Time: 24-48 hours]
Level of pro- and anti-inflammatory cytokines (IL-1, IL-6, IL-8, IL-10, tumor necrosis factor-alfa, procalcitonin)  |
| 2   | Doses of vasopressors and / or inotropes ( $\mu$ g / h / kg bodyweight)
[Deadline: first 72 hours]  |
| 3   | Renal function [Time: first 72 hours] creatinine level   |
| 4   | Lactate level [Time: first 72 hours]   |
| Secondary results   |  |
| 1   | Inflammatory response - The level of C-reactive protein (CRP) [Time: 24-48 hours]
The level of C-reactive protein (CRP) before the start of the operation, 2 hours after the start of the operation, when the operation is turned off, 24 hours after the shutdown of the operation |
| 2   | Inflammatory response - The level of leukocytes [Time: 24-48 hours]
The level of leukocytes before the start of the operation, 2 hours after the start of the operation, when the operation is turned off, 24 hours after the shutdown of the operation                             |

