| 3   | Inflammatory response - The level of procalcitonin [Time: 24-48 hours]
The level of procalcitonin before the start of the operation, 2 hours after the start of the operation, when the operation is turned off, 24 hours after the shutdown of the operation                       |

|                          |  |
|--------------------------|--|
| 4                 | Application and dosage of vasopressors [Deadline: first 48 hours]
Incidence of application and level of dosage of vasopressors on days 2 and 3 after surgery; |
| 5                 | Application and dosage of inotropes [Deadline: first 48 hours]
Incidence of application and level of dosage of inotropes on days 2 and 3 after surgery;       |
| Long-term results |  |
| 1                 | Length of stay in the intensive care unit [Duration: first 48 hours]   |
| 2                 | Length of hospital stay [Term: up to 1 month];   |
| 3                 | 30 day survival rate.  |

| For operations with prolonged cardio pulmonary bypass, hypothermia and circulatory arrest |  |
|--|--|
| Primary results   |  |
| 1   | Cytokine response [Time: 24-48 hours]
Difference of Cytokine response [Time: 24-48 hours]
Level of pro- and anti-inflammatory cytokines (IL-1, IL-6, IL-8, IL-10, tumor necrosis factor-alfa, procalcitonin, C-reactive protein) |
| 2   | SOFA-Score [Time Frame: 24, 48, 72 hours]
Sequential Organ Failure Assessment Score at 24, 48, 72 h (values from 6 to 24, where the higher values explain higher disease severity)  |
| 3   | Difference of mean arterial pressure [Time Frame: 24, 48, 72 hours]
Comparison of mean arterial pressure at 24, 48, 72 hours between between two interventions (CytoSorb and Jaftron)   |
| 4   | Difference of CVP [Time Frame: 24, 48, 72 hours]
Comparison of mean arterial pressure at 24, 48, 72 hours between between two interventions (CytoSorb and Jaftron)  |
| 5   | Level of Serum lactate [ Time Frame: 24, 48, 72 hours ]
Comparison of mean arterial pressure at 24, 48, 72 hours between between two interventions (CytoSorb and Jaftron)   |
| Secondary results   |  |
| 1   | Inflammatory response - The level of C-reactive protein (CRP) [Time: 24-48 hours]
The level of C-reactive protein (CRP) before the cardiopulmonary bypass 2 hours   |

|                          |  |
|--------------------------|--|

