| 2   | Based on the literature review, conduct a comparative assessment of the application of methods of extracorporeal hemoadsorption in                          | 2021 | 9 | Comparative evaluation will be carried out on the application of methods of extracorporeal hemoadsorption in pulmonary and heart failure   |  |  |

|     |  |      |    |  |   |   |
|-----|--|------|----|--|---|---|
|     | pulmonary and heart failure  |      |    |  |   |   |
| 3   | Patient recruitment  | 2021 |    | Patient recruitment for the study will begin   | Patient recruitment will continue   | Patient recruitment will continue   |
| 3.1 | Recruiting of patients using extracorporeal life support systems as an organ-substituting aid for heart and pulmonary failure. | 2021 | 36 | Recruiting of patients using extracorporeal life support systems as an organ-substituting aid for heart and pulmonary failure. | Recruiting of patients when using extracorporeal life support systems, as an organ-substituting aid, with heart and pulmonary failure will continue | Recruiting of patients when using extracorporeal life support systems, as an organ-substituting aid, with heart and pulmonary failure will continue |
| 3.2 | Recruiting of patients for implantation of mechanical circulatory devices using an extracorporeal cytokine adsorber            | 2021 | 36 | Recruiting will begin patients with implantation of mechanical circulatory devices using an extracorporeal cytokine adsorber   | Recruiting patients for implantation of mechanical circulatory devices using an extracorporeal cytokine adsorber will continue                      | Recruiting patients for implantation of mechanical circulatory devices using an extracorporeal cytokine adsorber will continue                      |
| 3.3 | Recruiting of patients for hypothermia and cardiopulmonary bypass reconstruction with an extracorporeal cytokine               | 2021 | 36 | Will be started recruiting of patients for reconstructions of the aortic arch with hypothermia and cardiopulmonary bypass      | Recruiting of patients for hypothermia and cardiopulmonary bypass reconstruction with an extracorporeal cytokine                                    | Recruiting of patients for hypothermia and cardiopulmonary bypass reconstruction with an extracorporeal cytokine                                    |

|     | adsorber  |      |    | using an extracorporeal cytokine adsorber  | adsorber will continue   | adsorber will continue   |

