|   | operations with long-term artificial circulation, hypothermia and circulatory arrest, as an organ-substituting aid |      |    | reconstruction of the aortic arch with long-term artificial circulation and hypothermia, as an organ-replacing aid | reconstruction of the aortic arch with long-term artificial circulation and hypothermia, as an organ-replacing aid                 | reconstruction of the aortic arch with long-term artificial circulation and hypothermia, as an organ-replacing aid                 |
| 5 | Analysis of clinical and laboratory data on the restoration of organ function using innovative technologies        | 2022 | 24 |  | An analysis of clinical and laboratory data on the restoration of organ function will be carried out using innovative technologies | An analysis of clinical and laboratory data on the restoration of organ function will be carried out using innovative technologies |
| 6 | Statistical processing and analysis of the obtained data   | 2022 | 24 |  | Statistical processing of the obtained research results will be carried out  | Statistical processing of the obtained research results will be carried out  |
| 7 | Determination of an effective method of treating heart and pulmonary failure using organ replacement technologies. | 2023 | 12 |  |  | An effective method will be determined of the treatment of heart and pulmonary failure using organ replacement technologies        |
| 8 | Development of innovative methods of   | 2022 | 24 |  | Innovative methods of treating patients using  | Innovative methods of treating patients using organ-   |

|    |  |      |    |                                 |   |   |
|----|--|------|----|---------------------------------|---|---|
|    | treating patients using organ-replacing technologies                             |      |    |                                 | organ-replacing technologies will be developed                  | replacing technologies will be developed  |
| 9  | Development of practical protocols for the restoration of organ function         | 2022 | 24 |                                 | Practical protocols to restore organ function will be developed | Practical protocols to restore organ function will be developed                   |
| 10 | Implementation of patient treatment protocols using organ-replacing technologies | 2023 | 12 |                                 |   | Patient treatment protocols using organ-replacing technologies will be introduced |

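### The methods text makes cytokine measurement depend on a clinical difference between the arms, while the outcome tables list the same cytokines as an unconditional primary result

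*Combined protocol and SAP*

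**What the plan says.** **Methods text.** In section 4 (Research methods and ethical issues), in the text under the subheading on retrospective artificial-heart patients, the plan states: "The level of cytokines (IL-1, IL-6, IL-8, IL-10, tumor necrosis factor alpha) and complements will be determined before, during and after" life support for heart and pulmonary failure, aortic arch surgery and mechanical circulatory support. The sentence ends with a condition: "if investigators find a corresponding difference between the two groups in terms of clinical variables".

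**Outcome tables** (Performance evaluation criterias). Row 1 of the primary results in each of the three tables is the cytokine response, and none of the three carries a condition:

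- Life support: the five cytokines, "before the implantation, 2 hours after the start of ECMO support, explantation of ECMO, 24 hours after explantation of ECMO".
- LVAD: "Level of pro- and anti-inflammatory cytokines (IL-1, IL-6, IL-8, IL-10, tumor necrosis factor-alfa, procalcitonin", with a 24-48 hour window and no sampling times.
- Prolonged bypass: "Level of pro- and anti-inflammatory cytokines (IL-1, IL-6, IL-8, IL-10, tumor necrosis factor-alfa, procalcitonin, C-reactive protein", again with only the 24-48 hour window.

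**Work plan** (section 8). Items 4.1, 4.4, 4.7 and 4.10 schedule blood sampling for cytokines in all three years, also without a condition. For years 2 and 3, item 3 says "Patient recruitment will continue", while item 6, "Statistical processing and analysis of the obtained data", starts in 2022 and runs 24 months.

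The study design table states that there is no masking.

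**The concern.** Whether a primary result is measured should not depend on what the other results show. Under the methods text there are two outcomes, and both are bad:

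1. No clinical difference is seen, and the five cytokines are not determined. Row 1 is then empty for life support, keeps only procalcitonin for LVAD, and keeps only procalcitonin and CRP for bypass. Both devices are described as removing or adsorbing cytokines. Yet where the condition applies, a difference or a similarity in cytokine levels without a clinical difference could not be observed.
2. A clinical difference is seen, and the cytokines are determined because of it. Any cytokine comparison then reported has been selected on other outcomes, and it cannot be read as independent support for them.

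The people who judge the condition know the allocation. The plan does not say which clinical variable counts, how large the difference must be, or when it is judged. Because recruitment and statistical processing overlap, it is also open whether partial or complete data would be used.

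**Working it through.** The plan gives no figure to reproduce here. The check compares the passages and then counts what is affected.

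**Step 1. Are these the same measurements?** The methods text names IL-1, IL-6, IL-8, IL-10 and TNF-alpha, plus complements. All three row 1 entries contain those five cytokines. The LVAD row adds procalcitonin; the bypass row adds procalcitonin and CRP. Complements appear in no outcome table. The overlap is therefore exactly the five cytokines.

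**Step 2. Does the methods sentence concern the randomised trial?** Its subheading refers to retrospective artificial-heart patients. The text beneath it, however, deals with two groups, a 72-hour intervention, the two adsorption columns, life support and arch surgery. That is the randomised trial, so the subheading does not remove the conflict.

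**Step 3. How many primary rows are affected?**

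| Table | Primary rows | Rows affected | Randomised patients |
|---|---|---|---|
| Life support | 7 | 1 | 2 x (10 + 10) = 40 |
| LVAD | 4 | 1 | 2 x 5 = 10 |
| Prolonged bypass | 5 | 1 | 2 x 25 = 50 |
| Total | 16 | 3 | 100 |

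Thus 3/16 = 19% of primary rows are affected, and 16 - 3 = 13 are not.

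**Step 4. How does the size depend on reading the sentence?** If the condition governs the whole sentence, 3 rows and 100 patients are affected. If it attaches only to the last item, mechanical circulatory support, and that means LVAD, 1 row and 10 patients are affected. The conflict shrinks but remains.

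**Step 5. Can the condition work as written?** The sentence asks for a level before the procedure. A pre-procedure level cannot wait for a difference that is seen later, unless blood is taken from everyone, stored and assayed afterwards. The plan describes no storage.

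**Step 6. Where is the pre-procedure cytokine level stated?** For life support it is in row 1 of the table. For LVAD and bypass (10 + 50 = 60 patients) row 1 gives only a window, and the methods sentence alone expressly calls for a cytokine level before the procedure. A correction that let the tables override the whole sentence would lose that sample.

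**The case against.** The strongest defence is that the condition is loose wording. Three outcome tables and four work-plan items point to unconditional measurement, and on its literal terms the condition cannot apply to a pre-procedure sample. The investigators may well intend to measure cytokines in everyone. This is plausible, but nothing in the plan confirms it. The work-plan items schedule sampling, not assay, so they fit unconditional measurement without contradicting the methods text.

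A second defence is the narrow reading in step 4. It limits the problem to the LVAD patients but does not resolve it.

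Three stronger readings are tempting and are not supported:

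- *The primary evaluation as a whole is lost.* It is not. Thirteen primary rows, including SOFA, mean arterial pressure, CVP, lactate, creatinine and vasopressor dose, carry no such condition. Nothing says that row 1 outranks the others; its position is list order.
- *The condition raises the trial's false-positive rate for cytokines.* It does not. The probability that the condition is met and a cytokine test is significant cannot exceed the probability that the test is significant. The harm is a missing or selectively obtained result.
- *The decision will be taken on interim data.* The overlap of recruitment and analysis allows this, but the plan does not say so.

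**Conclusion.** The plan is wrong as written. The methods text and row 1 of the primary tables give incompatible instructions for the five cytokines, and no other text settles which applies. The conflict covers 3 of 16 primary rows and all 100 randomised patients if the condition governs the whole sentence. It covers 1 row and 10 patients if it is confined to mechanical circulatory support in the sense of LVAD. The conclusion needs no statistical assumption; only its extent depends on how the sentence is parsed. It should be settled before samples are due, because a pre-procedure sample that was not taken cannot be recovered.

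**What to change.** 1. **Section 4.** Delete the condition for the five cytokines, and state that they are assayed in every randomised patient whatever the clinical results. Keep the sampling before, during and after the procedure, and align it for life support with the four times in row 1 of that table. Samples may be stored and assayed in one batch if the plan says so.
2. **Row 1 of the LVAD and bypass tables.** Replace the bare 24-48 hour window with explicit times that include the pre-procedure sample. The times already listed for CRP, leukocytes and procalcitonin in the same tables would serve.
3. **Complements.** They may stay conditional if labelled exploratory.
4. **If the condition on cytokines is intended,** remove them from the primary results in all three tables.

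**Cost.** The edits are the sentence in section 4 and row 1 of two tables. With the times in item 2, blood is taken when the same tables already call for it for other markers. The real cost is a firm commitment to run cytokine assays that the primary tables already call for, and that section 4 makes conditional. As a ceiling, assuming four times in every patient and no missed samples, this is 40 x 4 x 5 = 800 determinations for life support and 60 x 4 x 5 = 1,200 for LVAD and bypass, 2,000 in all.

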#### **Study design.**

Study type: interventional (clinical study)

Set of participants: 100 participants

Distribution: randomized

Interventional model: parallel

Masking: no

Primary Goal: Treatment

| Intervention team (1 group)  | Intervention / treatment (device)  |
|--|--|
| Extracorporeal hemoperfusion device will be installed in the device of the extracorporeal life support system for heart failure...
(10 patients)        | HA330 - Jafron Biomedical Co., Ltd., China
- extracorporeal hemocorrection, which is based on the removal of cytokines from whole blood by sorption on a special hemoabsorbent due to the peculiarities of its porous structure and inner surface, which is indicated in conditions where cytokine levels are extremely elevated. |
| Extracorporeal hemoperfusion device will be installed in the device of the extracorporeal life support system for pulmonary failure
(10 patients).      | HA330 - Jafron Biomedical Co., Ltd., China
- extracorporeal hemocorrection, which is based on the removal of cytokines from whole blood by sorption on a special hemoabsorbent due to the peculiarities of its porous structure and inner surface, which is indicated in conditions where cytokine levels are extremely elevated. |
| An extracorporeal hemoperfusion device will be installed in patients before / during the implantation of a left ventricular assist device
(5 patients). | HA330 - Jafron Biomedical Co., Ltd., China
- extracorporeal hemocorrection, which is based on the removal of cytokines from whole blood by sorption on a special hemoabsorbent due to the peculiarities of its porous structure and inner surface, which is indicated in conditions where cytokine levels are extremely elevated. |
| An extracorporeal hemoperfusion device will  | HA330 - Jafron Biomedical Co., Ltd., China   |

|   |  |
|---|--|
| be installed in patients during operations with prolonged cardiopulmonary bypass, hypothermia and circulatory arrest. (25 patients).  | - extracorporeal hemocorrection, which is based on the removal of cytokines from whole blood by sorption on a special hemoadsorbent due to the peculiarities of its porous structure and inner surface, which is indicated in conditions where cytokine levels are extremely elevated. |
| Intervention team (2 groups)   |  |
| Extracorporeal hemoperfusion device will be installed in the device of the extracorporeal life support system for heart failure.

(10 patients)                           | CytoSorb (CytoSorbents Corp., USA) - an extracorporeal cytokine adsorber is a biocompatible polymer with high adsorption capacity, which is indicated in conditions where cytokine levels are extremely elevated.  |
| Extracorporeal hemoperfusion device will be installed in the device of the extracorporeal life support system for pulmonary failure.

(10 patients)                       | CytoSorb (CytoSorbents Corp., USA) - an extracorporeal cytokine adsorber is a biocompatible polymer with high adsorption capacity, which is indicated in conditions where cytokine levels are extremely elevated.  |
| An extracorporeal hemoperfusion device will be installed in patients before / during the implantation of a left ventricular assist device

(5 patients)                   | CytoSorb (CytoSorbents Corp., USA) - an extracorporeal cytokine adsorber is a biocompatible polymer with high adsorption capacity, which is indicated in conditions where cytokine levels are extremely elevated.  |
| An extracorporeal hemoperfusion device will be installed in patients during operations with prolonged cardiopulmonary bypass, hypothermia and circulatory arrest. (25 patients) | CytoSorb (CytoSorbents Corp., USA) - an extracorporeal cytokine adsorber is a biocompatible polymer with high adsorption capacity, which is indicated in conditions where cytokine levels are extremely elevated.  |

